1 PROTOCOL SUMMARY

1.1 SYNOPSIS

Title:	A prospective, randomized, single-blinded superiority study to evaluate bone wax use for hemostasis during primary unilateral total knee arthroplasty
Study Description:	
Total joint arthroplasty can result in significant blood loss. Postoperative anemia has been associated with prolonged length of stay and increased hospital costs.¹ Minimizing blood loss has led to multiple blood conservation strategies in orthopaedic procedures.
 
Bone wax is a well-known topical hemostatic agent comprised of a mixture of beeswax, paraffin, and isopropyl palmitate. This inexpensive agent works by sealing the bleeding site and tamponades bleeding from the cancellous bone. Bone wax can be precisely applied evenly and stops bone bleeding immediately upon application.²
 
The purpose of this study is to assess whether the application of bone wax to exposed cancellous bone, after the cemented implants are in place, will provide superior hemostasis in total knee arthroplasty (TKA) patients compared to patients who do not have the bone wax applied. Hemostasis will be assessed by calculating blood loss using the Hb-balance formula.

	
This will be a prospective, randomized, single-blinded, superiority study in patients scheduled for a primary unilateral TKA with [name] or [name]. The restriction of this study to two surgeons will limit variations in the outcomes being measured due to differences in surgical technique.

Objectives:	
Primary Objective:
 
• Efficacy: To assess whether bone wax results in superior hemostasis in patients undergoing primary unilateral TKA• Safety: To compare the safety profile between the 2 cohorts 
Secondary Objective:
 
• To assess whether the objective and functional outcomes in patients undergoing primary unilateral TKA differ between the patient cohorts (use of bone wax vs no bone wax)• To assess if there is a difference in the reduction of the Hemoglobin (Hgb) and Hematocrit (Hct) between the patient cohorts

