Endpoints:	
Endpoints-Primary:
 
• Efficacy: To calculate estimated perioperative blood loss on POD 1 using the Hb-balance formula• Safety: To assess the patients for any device adverse events related to the use of bone wax 
Endpoints-Secondary:
 
• To calculate the Knee Society Scores (KSS), both objective and subjective scores, done preoperatively and 8 weeks postoperatively• To measure the difference between the preoperative and POD1 Hemoglobin (Hgb) and Hematocrit(Hct) values in the two patient cohorts

Study Population:	100 female and male patients (50 subjects in each arm) scheduled for unilateral total knee arthroplasty by Drs. [name] or [name]
Phase:	NA
Description of Sites/Facilities Enrolling Participants:	Department of Orthopaedics, Syosset Hospital
Description of Study Intervention:	Bone wax is a well-known topical hemostatic agent comprised of a mixture of beeswax, paraffin, and isopropyl palmitate. This inexpensive agent works by sealing the bleeding site and tamponades bleeding from the exposed cancellous bone. ²
Study Duration:	The study timeline is 18 months
Participant Duration:	Patients will be in the study from the date of consent until their 8 week postoperative visit.

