1.3 SCHEDULE OF ACTIVITIES (SOA)

VISIT WINDOW	PREOPERTIVE PERIOD	DAY OF SURGERY	HOSPITALIZATION	8 WEEK PO VISIT (SOC)	2 MONTH FOLLOW-UP PHONE CALL (SOC)
CONSENT	X				
DEMOGRAPHICS	X				
PRESURGICAL TESTING HISTORY & PHYSICAL (SOC)	X				
PREOPERATIVE KNEE SOCIETY SCORE	X				
CONFIRM INCLUSION/EXCLUSION	X				
RANDOMIZATION		X			
SURGEON TO GRADE AMOUNT OF EXPOSED BONE		X			
DAILY HGB/HCT (SOC)			X		
POSTOPERATIVE KNEE SOCIETY SCORE				X	
DEVICE ADVERSE EVENTS		X	X	X	X

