2.3 RISK/BENEFIT ASSESSMENT

2.3.1 KNOWN POTENTIAL RISKS

The surgical techniques used to promote hemostasis will be consistent for all patients, except for the use of bone wax applied to the exposed cancellous bone following insertion of the prosthesis. There is a potential that patients in the control arm could have increase bleeding. The following risks have been shown to be associated with the use of bone wax: failed bone healing, foreign body reaction, granuloma growth, thrombosis, infection, and nerve compression

There is a small risk of an unintended breach of confidentiality, as there is in any research study that collects subjects' health information.

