2.3.3 ASSESSMENT OF POTENTIAL RISKS AND BENEFITS

Shin and Moo have published on the use of bone wax in total knee arthroplasty, 296 and 50 patients respectively had bone wax used during their total knee replacement. Shin, et al found that no adverse reactions, including the development of infections or foreign body reactions, were observed after the application of bone wax, a finding consistent with those of Moo et al.⁵

Moo found the difference between the bone wax group and the control group with regards to transfusion requirements and adverse events following surgery did not reach significance with the numbers available; however, trends in favor of the use of bone wax were noted.²

Drs. [name] and [name] have been using bone wax on exposed cancellous bone for over 4 years. All surgical site infections are reported as part of the Northwell Health System quality metrics. Bone wax has been used in 1140 total knee procedures. For this time period superficial

infections were reported in 2 patients and 1 deep infection. Additionally, the surgeons have not had any other issues felt to be related to the bone wax in their patients during their long term follow-up visits. The surgeons technique is to apply the bone wax to the exposed cancellous bone after the implant has been cemented in place therefore eliminating the risk for any issues with bone ingrowth.

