Intraoperative blood management strategies will be consistent for all subjects to avoid any confounding factors which could affect postoperative transfusion requirements. Any patients unable to be treated according to the department treatment guidelines will be excluded from the study. Intraoperatively blood loss is minimized by anesthetic techniques, pharmacologic interventions, and surgical techniques, as per standard of care and department treatment guidelines.

The patient and the postoperative hospital staff will be blinded to the treatment arm. The OR staff will be trained not to discuss this information with the patient. During the transition of care from the OR to the Post Anesthetic Care Unit (PACU) the use of bone wax is not routinely included in the verbal patient report. The lack of this information is not required to effectively manage the patient in the postoperative period and will not affect patient care. Postoperatively medical care is managed by the hospitalist, medical doctors specializing in the care of hospitalized patients. Hgb and Hct are drawn daily during the patient's hospitalization as per the standard of care. These values will be used to calculate the Hb-balance Formula.

Blood loss will be calculated using the Hb-balance Formula. This method is being used to provide a more standardized method of calculating blood loss. Eipe and Ponniah showed that surgical blood loss was underestimated by 64% when clinical methods are used to assess blood-soaked sponges and blood lost to suction bottles and the vacuum drain.⁷

Following discharge patients will be followed in the outpatient surgical office according to the postoperative standard of care visit schedule. Results of the 2011 KSS Objective and Functional Outcome Measurements administered as part of standard of care at the 8 week postoperative visit, or the office visit closest to these time points will be collected for research purposes. Patients will be called at 56 days (+2weeks) from the date of surgery for any device related adverse events. This call is standard of care for the department. Three attempts will be made to reach the patient before they are considered "lost to follow-up".

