8 STUDY ASSESSMENTS AND PROCEDURES

8.1 EFFICACY ASSESSMENTS

This clinical trial does not require any study specific screening tests or procedures. Preoperative screening done as part of the standard of care for an arthroplasty patient will be used to determine patient inclusion and exclusion. Additionally, there are no required lab testing or procedures required for this clinical trial.

Following discharge patients will be followed in the outpatient office according to the postoperative standard of care visit schedule. The 2011 KSS Objective and Functional Outcome Measurements will be collected at the 8 week visit, or the office visit closest to these time points. Patients will be contacted via phone approximately 56 days from the date of surgery to capture any device related adverse events or other relevant patient outcomes. These KSS outcomes measures and follow-up phone calls are standard of care for the department.

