8.3.5 ADVERSE EVENT REPORTING

This clinical trial consists of postoperative total knee arthroplasty patients. DRE's common and expected in this group of patients include postoperative pain, nausea, hypotension, anemia, and dehydration. Events anticipated and expected in the postoperative arthroplasty patient will not be considered an adverse event for collection in the eCRF. Additionally, there are no study interventions for the control group. This group will be following the standard of care treatment for a total knee arthroplasty patient. Therefore, no adverse events related to the application of bone wax will be occurring in this group.

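### The primary safety objective compares the arms, but its only endpoint is zero in controls by construction, and the capture rules do not clearly secure a control-arm count

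*Combined protocol and SAP*

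**What the plan says.** The primary safety objective in 1.1 and 3 is "To compare the safety profile between the 2 cohorts". The justification column in section 3 also looks across the two cohorts. The one endpoint listed for it, in both places, is "To assess the patients for any device adverse events related to the use of bone wax". Section 8.3.5 then says of the control group: "Therefore, no adverse events related to the application of bone wax will be occurring in this group".

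The rules on recording events point in different directions:

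- **8.3.4** asks for every adverse event on study to be documented whatever its relationship, puts non-serious events on the case report form, and has the investigator ask about events at each visit.
- **8.3.5** keeps events that are expected after arthroplasty out of the eCRF. It gives five examples (pain, nausea, hypotension, anemia, dehydration) but does not close the list.
- **8.3.1** opens the reporting period when bone wax is applied.
- **8.3.2** requires reporting of deaths and serious injuries that the device may have caused or contributed to.
- **8.3.3.1** provides for capture of non-serious events judged related to the device.
- **1.3** has one safety row, "DEVICE ADVERSE EVENTS", from the day of surgery onward and not limited to one arm.
- **4.2** describes the follow-up call this way: "Patients will be called at 56 days (+2weeks) from the date of surgery for any device related adverse events". **8.1** describes the same call more widely: "to capture any device related adverse events or other relevant patient outcomes".
- **10.1.9.1** names agent-related events among the data entered in REDCap.

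Section 2.3.1 lists the risks associated with bone wax: "failed bone healing, foreign body reaction, granuloma growth, thrombosis, infection, and nerve compression". Section 9.4.4 plans descriptive reporting of adverse events and names neither the events nor a contrast between arms.

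**The concern.** A comparison needs a quantity that can take a value in both arms. Attribution to bone wax cannot do so where no wax is used. Infection and thrombosis, both on the 2.3.1 list, also occur without wax. A wax-arm count of either means little without a concurrent control count, and the stated endpoint does not supply one.

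The trial could still hold the data, because 8.3.4 asks for all events. But staff who follow 8.3.1 and 8.3.5 could reasonably record nothing for a control patient's complication: that patient has no start to the reporting window and no event attributable to the device. Control events not captured at the time may be hard to recover. At stake is whether one of the two primary objectives can be answered at all.

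**Working it through.** **Logic of the endpoint.** The objective is a contrast between arms. The endpoint is the count of wax-related events. By 8.3.5 the control value is 0 of 50, apart from a control patient who receives wax and is analysed as randomized (9.3). The wax count is 0 or more. The only possible results are a tie or more events with wax.

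**Which rule secures a control count?** Only 8.3.4 clearly does. The 8.3.1 window has no start for a patient without wax, although 1.3 schedules assessment from the day of surgery. The expected-event exclusion in 8.3.5 is open-ended. Sections 1.3, 4.2, 8.3.3.1 and 10.1.9.1 speak of device- or agent-related events, without saying that only these are recorded. No section ranks these rules.

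**The plan's own figures.** The plan states no event rate, sample size or power for safety, so there is no safety figure to reproduce. Its power table in 9.2 concerns blood loss; it reproduces to within about one percentage point and does not bear on this point.

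**Size at the site's infection rate.** Section 2.3.3 gives 1140 knees treated with wax; its superficial "infections were reported in 2 patients and 1 deep infection", that is 2 + 1 = 3. The rate is assumed equal in both arms, with n = 50 per arm (9.2).

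- p = 3/1140 = 0.263%; expected infections per arm = 50p = 0.13.
- P(at least one in an arm) = 1 − (1 − p)^50 = 1 − 0.8766 = 12.3%. This is also the chance of at least one control infection that the endpoint leaves out.
- Endpoint as written, control fixed at 0: P(control > wax) = 0%. P(wax > control) = 12.3% if every wax-arm infection is called related, and 1 − (1 − p/2)^50 = 6.4% if half are. The 12.3% is an upper bound, because 8.3.3.2 allows an event to be classed as not related when another cause is established.
- All-cause counting, two independent Binomial(50, p) counts: P(tie) = Σ P(X = k)² = 0.8766² + 0.1156² + 0.0075² + … = 78.2%. Each direction is (1 − 0.782)/2 = 10.9%.

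**Other rates, for illustration only.** The documents give no all-cause complication rate, so these are assumptions, again equal in both arms.

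| Assumed rate | Expected control events | P(at least one control event left out) | All-cause: P(one given arm shows more) |
|---|---|---|---|
| 1% | 0.5 | 39.5% | 26.7% |
| 2% | 1.0 | 63.6% | 34.5% |
| 5% | 2.5 | 92.3% | 40.6% |

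At each rate the chance that controls show more is 0% under the endpoint as written. Since 9.4.4 is descriptive, none of these is a type I error rate.

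**The case against.** The strongest reply is that control events are largely provided for. Section 8.3.4 is not limited to one arm and asks for all events regardless of relationship. A category for unrelated events in 8.3.3.2 makes sense only if such events are recorded. Section 9.4.4 refers to adverse events in general. Section 8.3.2 governs reporting to outside bodies, not entry on the case report form, and the control-arm sentence in 8.3.5 is close to a truism. None of the 2.3.1 risks is among the named exclusions in 8.3.5. Section 2.3.3 says surgical site infections are reported through the health system's quality metrics, so infections at least might be recovered. And with 0.13 infections expected per arm, 50 patients per arm say little about safety under any endpoint.

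Much of this stands. It would be wrong to say that control events are not collected, and infection is the easiest complication to recover later. Low counts do limit what any safety comparison can show: all-cause counting still ties 78.2% of the time at the site's infection rate. But none of it changes the endpoint in 1.1 and 3, and none of it says whether 8.3.4 prevails over 8.3.1, 8.3.3.1 and 8.3.5. Low counts reduce precision; the endpoint as written removes the comparator.

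**Conclusion.** The concern holds. As written, a primary objective cannot be answered by its own endpoint: the control count is 0 of 50 by construction, and whether the database holds an all-cause control count depends on which section staff follow. At the site's infection rate the loss is mainly one-sided. The chance of controls showing more events falls from 10.9% to 0%, while the chance of wax showing more hardly moves (at most 12.3%, against 10.9%). These figures rest on equal rates in the two arms, on a historical rate that covers infection only in wax-treated knees, and on no control patient receiving wax. No stated figure is wrong, and the sample size and primary efficacy analysis are unaffected. This should be fixed before enrolment.

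**What to change.** 1. In 1.1 and 3, define the primary safety endpoint as the number of patients in each arm with any prespecified complication, regardless of cause, from surgery to the 8-week contact. The components are those already listed in 2.3.1: "failed bone healing, foreign body reaction, granuloma growth, thrombosis, infection, and nerve compression". Give each a short working definition. Record relatedness as a separate field with the 8.3.3.2 categories.
2. In 8.3.1, start the reporting window at the same surgical time point in both arms.
3. Reconcile 8.3.4 and 8.3.5. State that the expected-event exclusion applies equally in both arms and cannot remove a prespecified complication, serious or not. Align 1.3, 4.2, 8.1, 8.3.3.1 and 10.1.9.1 with this.
4. In 9.4.4, report these counts by arm descriptively, and exempt safety from the formal testing that 9.4.1 promises for all outcomes other than baseline.

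The cost is protocol wording and a six-item checklist on the adverse event form. The hospital record, 8-week visit and phone call already exist for both arms. The downside is a slightly longer form.

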8.3.6 SERIOUS ADVERSE EVENT REPORTING

The study investigator shall complete an Unanticipated Adverse Device Effect Form and submit to the reviewing Institutional Review Board (IRB) as soon as possible, but in no event later than 5 working days after the investigator first learns of the effect. The investigator is responsible for conducting an evaluation of an unanticipated adverse device effect and shall report the results of such evaluation to the Food and Drug Administration (FDA). Thereafter, the investigator shall submit such additional reports concerning the effect as FDA requests.

8.3.7 REPORTING EVENTS TO PARTICIPANTS

Not Applicable

8.3.8 EVENTS OF SPECIAL INTEREST

Not Applicable

8.3.9 REPORTING OF PREGNANCY

Not Applicable

8.4 UNANTICIPATED PROBLEMS

8.4.1 DEFINITION OF UNANTICIPATED PROBLEMS (UP)

The Office for Human Research Protections (OHRP) considers unanticipated problems involving risks to participants or others to include, in general, any incident, experience, or outcome that meets all of the following criteria:

- Unexpected in terms of nature, severity, or frequency given (a) the research procedures that are described in the protocol-related documents, such as the Institutional Review Board (IRB)-approved research protocol and informed consent document; and (b) the characteristics of the participant population being studied;
- Related or possibly related to participation in the research (“possibly related” means there is a reasonable possibility that the incident, experience, or outcome may have been caused by the procedures involved in the research); and
- Suggests that the research places participants or others at a greater risk of harm (including physical, psychological, economic, or social harm) than was previously known or recognized.

This definition could include an unanticipated adverse device effect, any serious adverse effect on health or safety or any life-threatening problem or death caused by, or associated with, a device, if that effect, problem, or death was not previously identified in nature, severity, or degree of incidence in the investigational plan or application (including a supplementary plan or application), or any other unanticipated serious problem associated with a device that relates to the rights, safety, or welfare of subjects (21 CFR 812.3(s)].

8.4.2 UNANTICIPATED PROBLEM REPORTING

The investigator will report unanticipated problems (UPs) to the reviewing Institutional Review Board (IRB). The UP report will include the following information:

- Protocol identifying information: protocol title and number, PI's name, and the IRB project number;
- A detailed description of the event, incident, experience, or outcome;
- An explanation of the basis for determining that the event, incident, experience, or outcome represents an UP;
- A description of any changes to the protocol or other corrective actions that have been taken or are proposed in response to the UP.

To satisfy the requirement for prompt reporting, UPs will be reported using the following timeline:

- UPs that are serious adverse events (SAEs) will be reported to the IRB within 5 working days of the investigator becoming aware of the event.

- Any other UP will be reported to the IRB within 5 working days of the investigator becoming aware of the problem.
- All UPs should be reported to appropriate institutional officials (as required by an institution's written reporting procedures), the supporting agency head (or designee), and the Office for Human Research Protections (OHRP) within 30 days of the IRB decision.

8.4.3 REPORTING UNANTICIPATED PROBLEMS TO PARTICIPANTS

Not Applicable

9 STATISTICAL CONSIDERATIONS

○ 9.1 STATISTICAL HYPOTHESES

- Primary Efficacy Endpoint(s):

The primary endpoint is estimated total blood loss measured on POD 1, as calculated by Hb-Balance formula. Blood loss is measured in the morning prior to receiving anticoagulant treatment. We hypothesize that applying bone wax during TKA will reduce blood loss on POD 1.

- Secondary Efficacy Endpoint(s):

The secondary endpoints are hemoglobin and hematocrit from preoperative to POD 1, as well as, the Knee Society Score (KSS), which is collected preoperatively and 8 weeks postoperatively. There are two KSS scores; namely, (1) the patient's self-assessment of pain, expectations and functional outcomes, as well as, (2) the surgeon's objective measurements.

We hypothesize that applying bone wax during TKA will reduce the quantity of change in hemoglobin and hematocrit from preoperative to POD 1.

We hypothesize that applying bone wax during TKA will positively impact KSS; namely, a reduction in pain, an increase in functional outcomes and an increase in alignment, range of motion and stability at 8 weeks postoperative.

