2 INTRODUCTION

2.1 STUDY RATIONALE

Total joint arthroplasty can result in significant blood loss. Bone wax is a well-known topical hemostatic agent comprised of a mixture of beeswax, paraffin, and isopropyl palmitate. This inexpensive agent works by sealing the bleeding site and tamponades bleeding from the exposed cancellous bone.²

The purpose of this study is to assess whether the application of bone wax to the exposed cancellous bone, after the cemented implants are in place, will provide superior hemostasis in a total knee arthroplasty patients compared to patients who do not have the bone wax applied. Hemostasis will be assessed by calculating blood loss using the Hb-balance formula.

This will be a prospective, randomized, single-blinded, superiority study in patients scheduled for a primary unilateral TKA with [name] or [name]. The restriction of this study to two surgeons will limit variations in the outcomes being measured due to differences in surgical technique. The application of bone wax to the exposed cancellous bone has been the standard of care for four years by Drs. [name] and [name]. The surgeons technique is to apply the bone wax to the exposed cancellous bone after the implant has been cemented in place thereby eliminating the risk for any issues with bone ingrowth.

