6 STUDY INTERVENTION

6.1 STUDY INTERVENTION(S) ADMINISTRATION

6.1.1 STUDY INTERVENTION DESCRIPTION

Bone Wax is commercially available and is being used in accordance with approved labeling. During total joint arthroplasties bone wax is softened and applied firmly on the exposed cancellous bone around the prostheses by the orthopaedic surgeon after implant cementing. . (Appendix C-Bone Wax Package Insert)

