6.3 MEASURES TO MINIMIZE BIAS: RANDOMIZATION AND BLINDING

The Biostatistics Unit will develop a randomization procedure using a permuted block design within the Biostatistics Randomization Management System (BRMS) system. Additional details of the procedure, including required record keeping, will be further developed upon approval of this protocol. The Biostatistics Unit has extensive experience in implementing and in producing detailed documentation for such procedures. The patient will be blinded to their randomization group.

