6.4 STUDY INTERVENTION COMPLIANCE

The surgeon and the operating room staff will be notified of the treatment arm prior to the start of the surgery. All patient outcome measurements are part of the standard of care for a total knee arthroplasty patient.

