9.4.3 ANALYSIS OF THE SECONDARY ENDPOINT(S)

Separate linear mixed models for repeated measures will be used to compare each secondary outcome of interest (hemoglobin, hematocrit and KSS) between the treatment and control groups over time from preoperative to postoperative. An appropriate transformation will be used for any outcome that does not meet standard assumptions of Normality.

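### The objective Knee Society Score is the surgeon's own measurement, the surgeon knows the arm, and section 9.4.3 tests it like a laboratory value, so a claimed benefit on that score is open to detection bias.

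*Combined protocol and SAP*

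**What the plan says.** Section 9.1 names two KSS scores. One is "the patient's self-assessment of pain, expectations and functional outcomes". The other is "the surgeon's objective measurements". For both it states a hypothesis in favour of wax at 8 weeks, and for the second this concerns stability, alignment and range of motion.

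On who knows the arm, section 6.4 says: "The surgeon and the operating room staff will be notified of the treatment arm prior to the start of the surgery". Section 6.1.1 has the wax applied "by the orthopaedic surgeon after implant cementing". Section 4.2 says: "The patient and the postoperative hospital staff will be blinded to the treatment arm". Section 6.3, on measures against bias, names only the patient: "The patient will be blinded to their randomization group". Sections 4.2 and 8.1 place the 8-week KSS at an outpatient office visit under usual care. Neither says that the person measuring is kept unaware of the arm.

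On the analysis, section 9.4.3 says: "Separate linear mixed models for repeated measures will be used to compare each secondary outcome of interest (hemoglobin, hematocrit and KSS". Section 9.4.1 applies p < 0.05 to all analyses. Neither section separates the two KSS scores by whether the rater is blinded, or says which of them would support a claim.

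**The concern.** The two KSS scores differ in their protection against bias. The patient who completes one does not know the arm. The surgeon credited with the other was told the arm and applied or withheld the wax. Section 2.1 also records the surgeons' prior practice: "The application of bone wax to the exposed cancellous bone has been the standard of care for four years". Knowledge of the arm together with a preference for one treatment is the usual setting for detection bias. It does not show that bias will occur.

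KSS is not incidental to this trial. Section 2.2 gives the lack of such outcomes in the earlier bone wax studies as one of the gaps this trial should fill, and the objective outcome is part of the secondary objective in section 3. As the plan stands, a significant difference on the surgeon-measured score could be reported as a benefit of wax with nothing in the plan to qualify it.

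**Working it through.** **Who is blinded for which outcome**

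| Outcome | Source of the value | Does that source know the arm? |
|---|---|---|
| Blood loss on POD 1 (primary) | Formula from laboratory hemoglobin (4.2, 9.1) | Not exposed to a rater |
| Hemoglobin, hematocrit | Laboratory (4.2) | Not exposed to a rater |
| KSS, patient-reported | Patient (9.1) | No (4.2, 6.3) |
| KSS, objective, preoperative | Surgeon (9.1) | No: taken before randomization (1.3) |
| KSS, objective, 8 weeks | Surgeon (9.1; inferred for this visit) | Yes (6.4, 6.1.1), unless masked by a step the plan does not describe |

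Only the last row is exposed.

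**The plan's own figures**

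The documents give no SD, effect size or power for KSS. The only figures are those for blood loss in section 9.2, and they serve to confirm the test. For a two-sided two-sample t-test at 0.05 with n = 50 per arm (98 df), the noncentrality is difference / (SD × √(2/n)), and √(2/50) = 0.2. Row 1 gives 153 / (271.5 × 0.2) = 2.82 and a power of 79.7%, against 80% stated. The five rows give 79.7%, 95.4%, 82.3%, 91.0% and 80.8%, against 80%, 95%, 82%, 91% and 81%. The table reproduces with a two-sided test.

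**What a rating shift would do**

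Suppose there is no true effect and knowledge of the arm moves the wax-minus-control difference by b SD of the 8-week score. The noncentrality is b / 0.2. The values of b are assumptions.

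| b (SD) | Noncentrality | Chance of two-sided p < 0.05 | Of which in favour of wax |
|---|---|---|---|
| 0 | 0 | 5.0% | 2.5% |
| 0.1 | 0.5 | 7.9% | 7.2% |
| 0.2 | 1.0 | 16.8% | 16.6% |
| 0.3 | 1.5 | 31.8% | 31.8% |

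**Dependence on the model**

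Section 9.4.3 plans a mixed model from before to after surgery, not a t-test. Let r be the correlation between the preoperative and 8-week scores (also assumed). A comparison of change has relative SD √(2 − 2r). A baseline-adjusted comparison has relative SD √(1 − r²).

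| r | Change: b = 0.1 / 0.2 / 0.3 | Baseline-adjusted: b = 0.1 / 0.2 / 0.3 |
|---|---|---|
| 0.3 | 7.0% / 13.3% / 24.1% | 8.1% / 18.0% / 34.4% |
| 0.5 | 7.9% / 16.8% / 31.8% | 8.8% / 20.8% / 40.3% |
| 0.7 | 9.8% / 24.8% / 48.3% | 10.7% / 28.4% / 54.8% |

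At r = 0.5 the change analysis equals the t-test, because √(2 − 1) = 1. No choice of model removes the shift, and a more precise one detects it more often. For the patient-reported score the surgeon's shift is zero, so this source of error leaves the rate at 5%.

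**The case against.** Much of the case on the other side stands.

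- A surgeon who applies or omits wax cannot be blinded during the operation. The documents say openly who is blinded and who is not, so the single-blinded label is not a contradiction.
- No passage states that the operating surgeon personally takes the 8-week measurement. Sections 4.2 and 8.1 say only that KSS is obtained at an office visit. The wording of 9.1 makes the surgeon the natural reading, but it is an inference. The KSS form (Appendix B) is not in the text reviewed, so the room for judgement in its items cannot be assessed.
- KSS is secondary, with no testing hierarchy and no sample-size basis. The objective score has little formal confirmatory standing to lose.
- The false-positive rates are general arithmetic for any shifted outcome with 50 per arm. They are not evidence that a shift exists here.

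A reader might also infer three stronger points that the documents do not support. The first is that the trial's conclusion on function is biased; section 9.1 places pain and function in the patient's own score, and the patient is blinded. The second is that the two scores will be merged; 9.1 names two scores, sections 1.1 and 3 ask for both, and no passage plans a sum. The third is that the bias can be removed by wording alone; relabelling the objective score changes what is claimed from it, not how it was measured.

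One point remains unanswered. Section 9.4.3 says only KSS, and nothing in the plan stops a benefit claim from resting on the score whose rater knows the arm.

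**Conclusion.** The point holds for the objective KSS at 8 weeks and for nothing else. A claim that wax improves stability, alignment or range of motion would rest on a measurement attributed to someone who knows the arm, tested with no distinction from laboratory outcomes. The primary endpoint, the hemoglobin and hematocrit comparisons and the patient-reported KSS are not exposed to this assessor bias.

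The size of any bias cannot be estimated from the documents. The rise from 5% to about 8%, 17% or 32% rests on assumed shifts of 0.1, 0.2 or 0.3 SD, 50 per arm, no true effect and a two-sided t-test. Across the mixed-model variants shown, a shift of 0.2 SD gives about 13% to 28%. The conclusion also assumes that the surgeon takes the 8-week measurement. If someone unaware of the arm does so, one sentence saying this settles the matter. This is a cheap improvement to a secondary analysis, not a threat to the trial's main result.

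**What to change.** In sections 9.1 and 9.4.3:

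1. State that the patient-reported and surgeon-measured KSS are analysed in separate models.
2. Name the patient-reported score at 8 weeks as the one on which any claim of KSS benefit rests.
3. Report the surgeon-measured score as supportive, labelled *assessor not blinded* wherever it appears.
4. State who takes the 8-week objective measurement and whether that person knows the arm.

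This needs no staff, visits or additional data. The cost is that the objective half of the secondary objective is answered with supportive evidence only, and the objective score itself stays exposed.

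Removing the bias from the objective score would require a measurer who does not know the arm. With two study surgeons, each could measure the other's patients if kept unaware of the arm. The documents do not show whether this is feasible, so it is an option and the fix does not depend on it.
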